This intervention, *Clozapine CHAMPION-ECHO (Center for Help and Assistance for Maryland Prescribers-Improving Outcomes Network using Extension for Community Healthcare Outcomes*, will be referred to as “CHAMPION” throughout the application. To minimize ANC monitoring barriers and maximize recruitment, we will provide Food and Drug Administration (FDA)-approved ANC point of care (POC) monitoring devices to all study sites, including those in the control condition (the PI and clinical team has used this previously). We will enroll at least 300 prescribers and additional clinical team members (up to 300) from approximately 60 outpatient mental health clinics (OMHCs) and other treatment sites. Individual prescribers can also enroll. Approximately half the sites/individuals will be randomized to CHAMPION and half randomized to enhanced treatment as usual (ETAU).

SPECIFIC AIMS

Aim 1:

To determine the effect of 12 months of CHAMPION exposure on: a) the clozapine prescribing practices of prescribers/clinical team; and b) the persistence of their patients use of prescribed clozapine. Hypothesis 1: Relative to the prescribers randomized to ETAU, prescribers randomized to CHAMPION will significantly increase the proportion of patients in their care who are prescribed clozapine as assessed using Maryland Medicaid prescription data. Hypothesis 2: For patients who are prescribed clozapine, the patients of prescribers randomized to CHAMPION will exhibit significantly greater persistence to clozapine treatment compared to patients of prescribers randomized to ETAU.

Aim 2:

To determine the effect of 12 months of CHAMPION exposure on prescriber knowledge and self-reported competence of prescribing clozapine and how those mechanisms of change are associated with increased clozapine prescribing and persistence of clozapine use. Hypothesis 3: Relative to the prescribers randomized to ETAU, prescribers randomized to CHAMPION will demonstrate significantly increased levels of clozapine knowledge and self-reported competence. Hypothesis 4: Prescriber self-reported competence will mediate the effect of CHAMPION on clozapine prescribing and persistence.

Exploratory Aims:

CHAMPION PROTOCOL

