b. Persistence to clozapine: Incident episodes of clozapine prescriptions will be identified by a 90 day look back period to identify a new episode of care. Persistence will be measured as the duration of the clozapine episode (in days) from the date of the first prescription record until the first gap of more than 45 days between prescriptions. Prescribing gaps will be calculated by first adding the days' supply to the dispensing date of each prescription to identify the date the prescription should be exhausted. Days that the patient is hospitalized will not be included in the calculation of episode duration. The first gap in prescribing of 46 days or more will be considered a discontinuation of the medication. An episode will only be right censored at the study endpoint, otherwise an episode can continue into the next time period. If a person has more than 1 episode of clozapine use during any time period, we will select the first episode.

Specific Aim 2: We will measure two educational outcomes: self-reported competence of prescribers/clinical team in using clozapine and knowledge associated with clozapine treatment. These will both be measured before and after the 12-month intervention period. These outcomes have been selected, because they are measurable and pilot data has already established that prescribers/clinical team will rate competence and answer questions on clozapine knowledge. In addition, we will pilot-test all questions and review the self-reported competence measure prior to the administration of the CHAMPION intervention.

a. Competence: Our measurement of competence will be based upon self-report assessment guided by Bandura's theory of self-efficacy (2, 3) and we are using a definition of competence as "the perceived self-efficacy rating of one's judgment to use clozapine"(2, 4). We will use a Visual Analog Scale (VAS) (0-100 mm) will serve as the primary outcome. Self-reported competence ratings will be evaluated for the overall use of clozapine and for each of the CHAMPION session topic areas. The VAS format has been found to be superior

CHAMPION PROTOCOL

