to using a standard Likert scale for self-reported competence evaluation (2). Self-efficacy ratings of competence have been shown to be increased in a mental health ECHO model (6); are recommended as a measure for approaching measurement of practice outcomes (7); and, when using VAS to measure self-efficacy competence, have been found to be a reliable and valid measure for this construct (8-10).

b. Knowledge: We will use multiple-choice questions (MCQ) to assess knowledge. The knowledge-based test questions will consist of 52 questions that will cover 2 questions per 26 topic areas and will conform to best practices and guidelines for design of the questions (11). MCQ have been used to assess knowledge with ECHO models (6, 12) and are known to be a reliable and valid measure for measuring knowledge (11). The total score will range from 0-52 correct answers.

Power

Hypothesis 1: Considering the intent to treat (ITT) approach to analyses, we will be able to assess administrative data prescription records for all prescriber participants regardless of their level of participation in the CHAMPION intervention sessions or other research data collections efforts. Missing data will be a concern only for those time periods where prescriber participants were not practicing in the Maryland public health system (before or after the intervention time period). We assume that we will have administrative data records from at least 85% of the prescribers/clinical team across all time points. We calculated the needed sample size using PASS version 13 (13) for independent proportions in a clustered-randomized design with the following specifications: alpha-level = .05, power = .80, effect size (h) = .39 (small to medium) and ICC = .01 (prescribers/clinical team nested within site). Effect size is based on estimating an 11% improvement in the rate of clozapine prescribing in CHAMPION; e.g. a 4% rate of clozapine prescribing in the ETAU group and a 15% rate in the CHAMPION condition. The required sample size is 254 based on clusters of 4-5 prescribers/clinical team per site.

Hypothesis 2: Even with a conservative estimate of the number of patients per prescriber on clozapine, a high ICC (.20) for patients nested within prescriber, and a small effect (d = .3), the power to detect differences in clozapine persistence between conditions is greater than 95%.

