Specific Aim 1, Hypothesis 2: *For patients who are prescribed clozapine, the patients of prescribers/clinical team randomized to CHAMPION will exhibit significantly greater persistence to clozapine treatment compared to patients of prescribers/clinical team randomized to the ETAU condition, as assessed using Maryland Medicaid prescription data.* Persistence (Approach Section 5b) will be measured as number of days of clozapine use. An episode will be identified as having begun during the 1 year prior to CHAMPION, during CHAMPION, or in the year after CHAMPION ends. A person can only have one episode in each of the time periods. We will use a generalized linear mixed-effects, 3-level model (SAS Proc GLIMIX, Poisson link), with a random site and a random prescriber effect to account for within site and within prescriber correlation (ICC). The longitudinal portion of the model will be treated as described for hypothesis 1. The test of hypothesis 2 will

CHAMPION PROTOCOL

operationally be the test of whether the coefficient of the CHAMPION/ETAU condition term is significantly greater than zero (two-sided test) at time 3. Post hoc analyses will use the same model to test for effects at time 2.

Specific Aim 2: To determine the effect of 12 months of exposure to the CHAMPION intervention on the knowledge and self-reported competence of prescribers/clinical team prescribing clozapine and how those mechanisms of change are associated with increased clozapine prescribing and persistence.

Specific Aim 2, Hypothesis 3: *Relative to the prescribers/clinical team randomized to the ETAU condition, prescribers/clinical team randomized to CHAMPION will demonstrate significantly increased levels of knowledge (correct number of MCQs) and self-reported competence (mean score on 0-100 mm VAS).*

Knowledge and competence are continuous measures that can be assumed to be normally distributed.

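### Hypothesis 2 compares persistence only among clozapine starters, a group formed after randomisation that CHAMPION is expected to enlarge, so the contrast alone cannot be read as an effect of CHAMPION on persistence

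*Combined protocol and SAP*

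**What the plan says.** The analysis section for Specific Aim 1, Hypothesis 2 states: "For patients who are prescribed clozapine, the patients of prescribers/clinical team randomized to CHAMPION will exhibit significantly greater persistence to clozapine treatment". The comparison group is the patients of ETAU prescribers.

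The outcome definitions (Primary Outcomes, Specific Aim 1, item b) fix who is counted: "Incident episodes of clozapine prescriptions will be identified by a 90 day look back period to identify a new episode of care". The Hypothesis 2 text assigns each episode to a period by its start date: "An episode will be identified as having begun during the 1 year prior to CHAMPION, during CHAMPION, or in the year after CHAMPION ends". Item b adds: "An episode will only be right censored at the study endpoint, otherwise an episode can continue into the next time period". The test is the CHAMPION/ETAU contrast at time 3, the year after the intervention, in a model with random site and prescriber effects and with time handled as for Hypothesis 1, that is, controlling for baseline.

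Under Specific Aims, Hypothesis 1 predicts that "prescribers randomized to CHAMPION will significantly increase the proportion of patients in their care who are prescribed clozapine". The Power section puts planning values on this: "a 4% rate of clozapine prescribing in the ETAU group and a 15% rate in the CHAMPION condition".

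Aim 1 presents both hypotheses as effects of 12 months of CHAMPION exposure. The plan states an ITT framework for all analyses (Missing Data). Apart from the race moderation analysis, its only provision for patient differences is an exploratory look at other site and patient variables (Exploratory Analyses).

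**The concern.** Every episode in the t=3 contrast begins after randomisation, and whether a patient has such an episode is what the intervention is designed to change. The two sets of starters are therefore not randomised groups. If CHAMPION brings clozapine to patients who would not otherwise have received it, the CHAMPION set contains a kind of patient that is missing from the ETAU set.

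Those additional patients might stop sooner, which could hide a real gain in persistence, or stay longer, which could create an apparent one. The more Hypothesis 1 succeeds, the larger their share, so the persistence contrast is hardest to interpret when the intervention works. The persistence part of Hypothesis 4 (mediation by competence) uses the same episodes and inherits the difficulty. No planned analysis would separate a change in persistence from a change in who was started.

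**Working it through.** **1. The plan's own figures.** The Hypothesis 1 inputs are "alpha-level = .05, power = .80, effect size (h) = .39 (small to medium) and ICC = .01". The arcsine effect size for 15% against 4% is h = 0.393, which agrees with .39. With h = .39, n is 103.2 per arm. With five per site the design effect is 1 + 4 × 0.01 = 1.04, which gives 216 in total after rounding up, and 216/0.85 = 254. The plan says "The required sample size is 254 based on clusters of 4-5 prescribers/clinical team per site", so the figure is reproduced if the 85% data-availability assumption was applied, which the text does not say.

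For Hypothesis 2 the plan claims power above 95% at d = .3 and an ICC of .20 for patients within prescriber. The number of clozapine patients per prescriber, m, is not given, so this cannot be checked outright. With 127 prescribers per arm and effective n = 127m/(1 + 0.20(m − 1)), power is 0.67 at m = 1, 0.87 at m = 2, 0.94 at m = 3, 0.952 at m = 3.4 and 0.98 at m = 5.

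**2. Whether anything in the plan restores comparability at t=3.**

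- Random site and prescriber effects deal with correlation, not with patient mix.
- Baseline control uses t=1 episodes, which began before CHAMPION could affect who started. It cannot adjust for a mix that changes later.
- The ITT statement keeps prescribers in their assigned arm. It does not make the patients they start on clozapine comparable.
- Patients who start during the CHAMPION year and are still on clozapine have no new t=3 episode, so the t=3 set is also shaped by persistence in the previous year.

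**3. How large a mix effect could be (illustration).** Two assumptions are needed that the documents do not supply: everyone treated under ETAU would also be treated under CHAMPION, and the planning rates, which are for any clozapine use, also hold for new starters. Let p0 = 4% and let p1 be the CHAMPION rate.

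- Share of CHAMPION patients who are additional: s = (p1 − p0)/p1.
- Arm difference when no patient's persistence changes: s × D, where D is the difference in mean persistence, in SD units, between additional and other patients.
- D that by itself produces d = .3: 0.3/s.

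| p1 | s | D needed |
|---|---|---|
| 6% | 2/6 = 33% | 0.90 SD |
| 8% | 4/8 = 50% | 0.60 SD |
| 10% | 6/10 = 60% | 0.50 SD |
| 15% | 11/15 = 73% | 0.41 SD |

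A smaller difference also matters. With D = 0.2 and p1 = 15%, the shift is 0.147 SD. The chance of a significant result with no effect on persistence is then about 21% at m = 1 and 50% at m = 5.

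**4. The same in days (assumed values, p1 = 15%).** Suppose patients treated under either arm average 300 days and CHAMPION changes nobody's persistence.

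- Additional patients at 200 days: the CHAMPION mean is (4 × 300 + 11 × 200)/15 = 227 against 300.
- Additional patients at 400 days: (4 × 300 + 11 × 400)/15 = 373 against 300.
- A true gain of 50 days in the other patients disappears if additional patients average 282 days: (4 × 350 + 11 × 282)/15 = 300 against 300.

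**5. What an all-patient measure can and cannot show.** Count clozapine days over all patients in the Hypothesis 1 denominator, with zero for those never prescribed it. Suppose persistence is 200 days for everyone and does not change: the means are 0.15 × 200 = 30 against 0.04 × 200 = 8. Now suppose additional patients average 300 days, again with no effect on anyone. The contrast among starters is (4 × 200 + 11 × 300)/15 = 273 against 200, and the all-patient measure is 0.04 × 200 + 0.11 × 300 = 41 against 8. Both favour CHAMPION although nobody's persistence changed.

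**The case against.** Hypothesis 2 is openly conditional on being prescribed clozapine. As a description of how long new episodes last in the two sets of practices it is valid, and a service planner may want exactly that. This stands, and it is why the comparison should be kept.

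The illustration also rests on borrowed rates. The 4% and 15% count any clozapine prescription in a period and so include long-term users, whereas Hypothesis 2 counts new episodes after a 90-day look-back. The 15% is itself only an example value. A reader might infer that 73% of the patients analysed under Hypothesis 2 have no ETAU counterpart. The documents do not support that: they give no rate of new starts, the share among starters could be higher or lower, and it falls to 33% at a 6% CHAMPION rate even under the same assumptions.

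A reader might also infer that Hypothesis 2 must be biased once Hypothesis 1 succeeds. That does not follow. Bias arises only if the additional patients differ in persistence, and nothing in the documents shows that they do, or in which direction.

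None of this answers the main point. The plan attributes the contrast to CHAMPION without saying which effect it estimates, and contains nothing that would reveal a shift in mix.

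**Conclusion.** The concern holds in a limited form. The t=3 persistence contrast is made within a group selected after randomisation by an event that CHAMPION is meant to alter. A difference, or the lack of one, may reflect patient mix and does not by itself establish an effect on persistence.

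The illustrated size is a required mix difference of 0.41 SD at a 15% CHAMPION rate, rising to 0.90 SD at 6%, to mimic the whole planned d = .3. This depends on the two assumptions in step 3 of the working. With no persistence SD and no data on additional starters, the actual size and direction are unknown.

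It is also tempting to think that agreement between Hypothesis 2 and an all-patient measure would confirm a persistence effect. Step 5 shows that it would not, because the all-patient measure will usually be positive whenever Hypothesis 1 succeeds.

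Hypothesis 1 does not select on clozapine and is not affected by this point.

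**What to change.** - Keep Hypothesis 2, but state that it compares starters and is not protected by randomisation. Limit its conclusion, and that of the persistence part of Hypothesis 4, accordingly.
- Report the characteristics of starters by arm and period: age, race, prior antipsychotic use and prior inpatient claims. These are among the Medicaid elements already being collected.
- Prespecify a sensitivity analysis that adjusts for those characteristics, or that bounds the result over a stated range of differences between additional and other starters.
- Add clozapine-covered days over all patients in the Hypothesis 1 denominator, with zero if never prescribed, labelled as the combined effect on starting and staying. Do not make a persistence claim depend on its agreement with Hypothesis 2.
- Preferably restrict that measure to patients attributed to study prescribers before randomisation, because the denominator is rebuilt in each period and its t=3 membership also forms after randomisation. Use a model suited to many zeros: at the planning rates, 85% to 96% of values would be zero.

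The cost is a little extra analysis of data already planned for, with no change to trial conduct. The price is a weaker conclusion for Hypothesis 2 and a companion measure that blends starting with staying.

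### Hypothesis 2 defines persistence as a right-censored duration, but the Poisson model for number of days does not carry the censoring, and the tested period has the shortest follow-up

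*Combined protocol and SAP*

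**What the plan says.** Under Primary Outcomes, item b (Persistence to clozapine), the definition begins "Persistence will be measured as the duration of the clozapine episode (in days"), counted from the first prescription record. Two further rules make it a time-to-event outcome: "The first gap in prescribing of 46 days or more will be considered a discontinuation of the medication", and "An episode will only be right censored at the study endpoint, otherwise an episode can continue into the next time period". Inpatient time is removed: "Days that the patient is hospitalized will not be included in the calculation of episode duration".

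Under Specific Aim 1, Hypothesis 2, persistence "will be measured as number of days of clozapine use". Episodes are assigned to a period by start date. The model is: "We will use a generalized linear mixed-effects, 3-level model (SAS Proc GLIMIX, Poisson link), with a random site and a random prescriber effect". The hypothesis is tested by whether the "condition term is significantly greater than zero (two-sided test) at time 3". On repeated periods the text says only "The longitudinal portion of the model will be treated as described for hypothesis 1"; Hypothesis 1 compares arms at t=3 controlling for baseline.

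The Power section claims more than 95% power for Hypothesis 2 with d = .3 and an ICC of .20 for patients within prescriber. It does not state the number of patients per prescriber or mention censoring. The Missing Data section expects little missing data for Hypotheses 1 and 2 and does not discuss open episodes.

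The endpoint is not given one date. Medicaid Data and Security gives both about June 2023 and about December 2023. The inpatient request under HMIS Data and Security ends on 31 July 2023. The ETAU section puts the end of observation in August 2023.

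**The concern.** The plan recognises censoring when it defines the outcome, then names a model with no visible place for it. A Poisson model for days takes each recorded duration as complete. Because episodes may run past their own period, follow-up depends on start date, and the period tested is the one followed least. Adjusting for t=1 does not cancel this, since t=1 episodes are followed about two years longer.

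At stake is one of the two Aim 1 outcomes described under Primary Outcomes, reused as a dependent variable in Hypothesis 4. A difference in days at t=3, or its absence, could reflect the data cutoff as well as the intervention.

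**Working it through.** **1. The plan's own figure.** Power = Φ(d/SE − 1.96), SE = √(2(1+(m−1)ρ)/(nm)), with d = .3 and ρ = .20 (Power section). I use n = 127 per arm (half the required 254) or 150 (planned). The two-sided .05 level is stated for Hypothesis 1 and assumed here. The number of patients per prescriber, m, is not given. For m = 1, n = 127: SE = √(2/127) = 0.1255, so power = Φ(2.39 − 1.96) = 67%.

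| m | 1 | 2 | 3 | 4 | 5 |
|---|---|---|---|---|---|
| Power, n = 127 to 150 | 67-74% | 87-92% | 94-97% | 97-98% | 98-99% |

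More than 95% therefore needs about 3-4 patients per prescriber, before any censoring. The stated figure can be neither confirmed nor refuted.

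**2. Follow-up by period.** With t=3 running from 1 August 2022 to 31 July 2023 (HMIS section), one-year periods before it and a July 2023 end, follow-up is about 730-1095 days at t=1, 365-730 at t=2 and 0-365 at t=3. A 31 December 2023 end adds 153 days, giving 153-518 at t=3.

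**3. Attenuation at t=3 (assumed durations).** Let T be exponential with mean μ in ETAU and μ/0.75 in CHAMPION (hazard ratio 0.75), and C uniform over the window. The expected share open is the average of e^(−C/μ); expected observed days are μ × (1 − share open). Share of log effect kept = log(ratio of observed days)/log(1/0.75).

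Example, July end, μ = 200: ETAU share open = (200/365)(1 − e^(−1.825)) = 0.460, so 108.1 days. CHAMPION share open = 0.545, so 121.4 days. Ratio 1.12; log effect kept = 0.116/0.288 = 40%.

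| Mean duration (days) | 90 | 200 | 400 | 730 |
|---|---|---|---|---|
| ETAU open, July | 24% | 46% | 66% | 79% |
| ETAU open, December | 4% | 21% | 45% | 64% |
| Ratio of observed days, July | 1.21 | 1.12 | 1.07 | 1.04 |
| Ratio of observed days, December | 1.27 | 1.18 | 1.10 | 1.06 |
| Log effect kept, July | 66% | 40% | 23% | 13% |
| Log effect kept, December | 84% | 56% | 34% | 20% |

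For mean 200 and a July end, 92% is kept at t=1, 75% at t=2 and 40% at t=3. Weibull durations with shape 0.7 show the same pattern.

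**4. Power if the standardised difference shrinks in proportion.** Without censoring, hazard ratio 0.75 gives d = 0.333/√((1 + 1.778)/2) = 0.283. The standardised difference in observed days is 0.52 and 0.33 of that (July, means 200 and 400), or 0.80 and 0.59 (December). Applied to d = .3 at m = 5, power is 55-62% and 26-30% (July), or 89-93% and 66-73% (December). For mean 90 and a December end it stays at 97-99%. All of this assumes valid standard errors.

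**5. Unequal start timing.** Keep ETAU starts even. Let CHAMPION start density fall linearly over t=3 from 1.25 to 0.75, or from 1.5 to 0.5, of its average, with no true effect. For means 200-400 and a July end, the ratio of observed days is 1.06-1.14. With 127 prescribers, m = 5, ICC .20 and valid standard errors, it is declared significant in 17-74% of trials (6-25% with a December end). With the stronger tilt reversed and a true hazard ratio of 0.75, the July ratio is 0.91-0.98, the wrong side of 1.

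**6. Variance.** Under the assumptions of step 3, the variance of observed days at t=3 is 58-89 times the mean; a Poisson model sets it equal to the mean given the random effects. I simulated no true effect with 254 prescribers in 60 sites, site log-SD 0.1, prescriber log-SD 0.54 and 200 trials per setting. The plain time-3 term gave 1.5-14.5% false positives. The t=3 comparison controlled for t=1, with no patient-level intercept, gave 80-93%. A separate simulation with a patient-level intercept gave 1-6%; its settings are not set out here, so that range is only indicative.

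**7. Does a censored model work?** In the same design with hazard ratio 0.75, an event model censoring open episodes 46 days before data end returned hazard ratios of 0.73-0.77. Its false positives under no effect were 2.5-10% (Monte Carlo error about 3 points). If open episodes are instead censored at data end itself, the t=3 hazard comes out 20-23% too low (July) or 4-12% too low (December), because a 46-day gap cannot be seen in the last 46 days.

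**The case against.** **Open episodes are named as censored.** This stands in part. The definition does class them so; that they would count as finished is an inference from the specified model. The exact statement is that the censoring rule is not carried into that model.

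**A reader might infer that the bias always runs towards no effect, and that a shared calendar window rules out false positives.** The documents do not support this. Both claims need start dates within t=3 to be alike in the two arms. CHAMPION is meant to change prescribing, and t=3 directly follows the sessions, so timing could differ. Step 5 shows that a false difference or a reversal is then possible. Crossing hazards could also change the direction.

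**A reader might infer that the planned test would miss a real benefit.** This is not shown. Step 4 uses valid standard errors, not those of the planned Poisson model. By step 6, one reading of the contrast produces mainly false positives.

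**The July end may be too pessimistic.** Hypothesis 2 uses Medicaid data, and the 31 July date comes from the inpatient request. The Medicaid section's concluding range runs to about December 2023, where attenuation is milder, and slight for short episodes.

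**Screening plots and transformations are planned.** They may reveal the excess variance, but the plan names no remedy for it, and they do nothing for censoring.

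**Conclusion.** The mismatch between a right-censored outcome and a model for completed days is in the plan's own text, and no other section repairs it. That t=3 has the shortest follow-up follows from the start-date rule. Shrinkage towards no effect is conditional on similar start timing in both arms and a CHAMPION hazard never above that of ETAU. Its size, from 13% to 84% of the log effect kept across the cases shown, rests on assumed exponential durations and a hazard ratio of 0.75.

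Whether the planned test would miss a benefit or give a false positive is not settled, because the t=3 contrast and the level of the random intercept are left open. It would also go too far to call the stated power wrong: it ignores censoring and rests on an unstated number of patients per prescriber, so it is unsupported. This should be fixed before analysis, but the evidence does not show that Hypothesis 2 is bound to fail.

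**What to change.** - **Model.** Analyse time to discontinuation (first gap of 46 days or more) with a clustered, censored model. Options are a piecewise Poisson or complementary log-log event model with a log person-time offset, in the same SAS procedure, or a Cox frailty model. Keep random site and prescriber effects, and add a patient effect for patients with episodes in more than one period. Leave hospital days out of time at risk, as the definition already does.
- **If a days scale is preferred.** Use a restricted mean with a fixed horizon, estimated by a method that handles censoring.
- **Censoring.** Censor open episodes 46 days before data end, or obtain 46 more days of claims to classify gaps. Consider also censoring at Medicaid disenrolment or death, where the data show them, so that these are not counted as discontinuation.
- **Specification.** State one study endpoint date and the exact t=3 contrast.
- **Linked text.** Use the same outcome model for the persistence part of Hypothesis 4. Restate Hypothesis 2 power with the assumed patients per prescriber and the expected censoring.

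The cost is revised SAP wording and modest programming, including a different mediation step for persistence, and at most 46 more days of claims. The effect becomes a hazard ratio instead of a ratio of days, and the stated power will probably look less favourable.
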